#### *Dabigatran etexilate Treatment Discontinuation for Elective Surgical Interventions*

Patients on dabigatran etexilate who undergo surgery or invasive procedures are at an increased risk for bleeding. Therefore, surgical interventions may require the temporary discontinuation of dabigatran etexilate.

**Preoperative Phase:** Due to an increased risk of bleeding dabigatran etexilate may be stopped temporarily, in advance of invasive or surgical procedures ([U11-1642-01](#)). If possible, dabigatran etexilate should be discontinued at least 24 hours before invasive or surgical procedures. In patients at higher risk of bleeding or in major surgery where complete haemostasis may be required, stopping dabigatran etexilate 2-4 days before surgery should be considered. A TT/dTT should be performed 6-12 hours before elective surgery and a normal result as defined by the local lab should be obtained before a patient undergoes surgery.

In patients, who develop renal insufficiency before the surgery, the recommendations summarized in the table below should be considered ([Table 4.2.1:1](#)). The decision to re-start treatment with dabigatran etexilate after the surgery is at the Investigator's discretion and can be started any time as soon as haemostasis has been achieved.

**Proprietary confidential information.**

© 2019 Boehringer Ingelheim International GmbH or one or more of its affiliated companies. All rights reserved.

This document may not - in full or in part - be passed on, reproduced, published or otherwise used without prior written permission.

Table 4.2.1:1 Recommendations on cessation of study drug in relation to the timing of surgery – under special consideration of the pharmacokinetics of dabigatran

Renal function (eGFR, mL/min)	Estimated half-life in hours (for dabigatran)	Stop study drug before surgery	
		High risk of bleeding 	Standard risk
>80	~13	2 days before	24 h before (2 doses)
≥50-80	~15 (12-18)	2-3 days before	1-2 days before
≥30 to <50	~18 (18-24)	4 days	at least 2 days (> 48 hours)
<30	~27 (>24 )	> 5 days	2-5 days

 In addition to renal function, high risk determinants of bleeding risk include type of surgery, comorbidities (e.g. major cardiac, respiratory or liver disease) and concomitant use of antiplatelet therapy. The type of surgery associated with a high risk of bleeding includes but is not limited to cardiac surgery, neurosurgery, abdominal surgery or those involving a major organ. Other procedures such as spinal anesthesia may also require complete hemostatic function.

The decision to use bridging therapy by UFH/LMWH during the peri-procedural period is left to the investigator's discretion and would depend on the bleeding and thrombotic risk in each patient.

#### *Dabigatran etexilate Treatment discontinuation for Acute Surgical Interventions*

If urgent surgery / acute intervention is required dabigatran etexilate should be temporarily discontinued. The surgery / intervention should be delayed at least 12 hours if possible after the last dabigatran etexilate dose. If surgery cannot be delayed there may be an increased risk of bleeding. The risk of bleeding should be weighed together with the urgency of the intervention. Local haemostasis and supportive care should be used during and after surgical intervention.

An elevated TT or dTT should lead the clinician to consider delaying surgery. If the TT/dTT test is not available, an aPTT, though less precise than the TT, can be used. A persistently prolonged thrombin time (TT or dTT) in the absence of heparin, fibrin / fibrinogen degradation products (e.g. with disseminated coagulation activation, sepsis, severe inflammation, and other conditions) or high concentrations of serum proteins (e.g. myeloma) suggests persistently elevated levels of dabigatran in the blood.

If a dabigatran specific reversal agent becomes available in a framework of clinical investigation during the conduct of this study and the patient fulfils the criteria for inclusion, it could be proposed to patients who require urgent reversal of dabigatran effects.

## 4.2.2 Restrictions

### 4.2.2.1 Restrictions regarding concomitant treatment

The following treatments should not be taken prior to dabigatran etexilate administration:

- Fibrinolytic agents - within 48 hours (Please note the following exception: the use of tissue plasminogen activator (t-PA) e.g. alteplase, or any other thrombolytic agents to re-establish patency of obstructed central venous line are allowed as long as the used dose is devoid of relevant systemic effects)
- P-glycoprotein inducers including but not limited to: Rifampicin, St. John's Wort, Carbamazepine, Phenytoin - within one week
- Asparaginase - within one week (or within 2 weeks in case of PEG-Asparaginase)

The following treatments should not be taken together with dabigatran etexilate:

- Any VKAs
- Therapeutic unfractionated heparin or LMWH (heparin flushes of indwelling catheters are allowed)
- Fibrinolytic agents (with the following exception: use of tissue plasminogen activators (t-PA) e.g. alteplase, or any other thrombolytic agents to re-establish patency of obstructed central venous line are allowed as long as the used dose is devoid of relevant systemic effects)
- P-glycoprotein inhibitors including but not limited to: Amiodarone, Cyclosporine, Dronedarone, Itraconazole, Ketoconazole, Nelfinavir, Quinidine, Ritonavir, Saquinavir, Tacrolimus, Verapamil
- P-glycoprotein inducers including but not limited to: Rifampicin, St. John's Wort, Carbamazepine, Phenytoin
- Asparaginase
- Any other investigational drug (with the exception of a specific reversal agent to counteract the antithrombotic activity of dabigatran etexilate where the patient is eligible to participate in a specific trial in a framework of clinical investigation)

Note: Intended extended use of anti-inflammatory agents or agents containing ASA should be avoided. Corticosteroids in general should be avoided but may be administered if they are part of a chemotherapy regimen given in cycles, or if the benefits of corticosteroid therapy clearly outweigh risks.

#### 4.2.2.2 Restrictions on diet and life style

Dabigatran etexilate may be taken with or without food. Dabigatran etexilate hard capsules should preferably be taken with a glass of water, if feasible to facilitate delivery to the stomach. If gastrointestinal symptoms develop it is recommended to take dabigatran etexilate with a meal and/or a proton pump inhibitor such as pantoprazole.

### 4.3 TREATMENT COMPLIANCE

Subjects or, if applicable, parents or legal guardians, will be asked to carefully complete a daily medication intake log for dabigatran. Subjects or, if applicable, parents or legal guardians, are requested to bring this completed log and all remaining trial medication to every clinic visit which they will attend. Empty dabigatran etexilate capsule containers, pellets boxes or solution vials must also be returned to the investigator's site for compliance calculation and disposal. Compliance will be calculated using the below equation preferably based on the returned medication (completed logs may also be used):

Compliance (in %) = (Actual number of dabigatran etexilate doses taken since last count / Planned number of dabigatran etexilate doses which should have been taken in the same period) X 100

If an interruption of dabigatran etexilate was medically required this would be considered by reducing the number of expected doses that "should have been taken" accordingly in the compliance calculation.

Unreliable subjects should not be entered in the study at the discretion of the investigator. Compliance during the treatment period should be between 80% and 120%. In cases where compliance is not achieved based on the above definition, the parent or legal guardian and when applicable the patient should be interviewed and re-informed about the purpose and the conduct of the trial and the importance to maintain good compliance. If non-compliance persists despite all possible efforts, patients should be removed from the treatment and alternative therapy should be proposed in such cases.

## 5. VARIABLES AND THEIR ASSESSMENT

### 5.1 EFFICACY

#### 5.1.1 Endpoints of efficacy

All criteria in this study will be considered as safety endpoints.

#### 5.1.2 Assessment of efficacy

Not applicable.

### 5.2 SAFETY

#### 5.2.1 Endpoint(s) of safety

##### Primary endpoints:

- Recurrence of venous thromboembolism (VTE) at 6 and 12 months
- Major and minor (including clinically relevant non-major (CRNM)) bleeding events at 6 and 12 months
- Mortality overall and related to thrombotic or thromboembolic events at 6 and 12 months

All elements of the primary endpoints will be assessed by qualified clinicians using an appropriate objective method and will be centrally adjudicated by an independent committee.

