**Proprietary confidential information.**

© 2019 Boehringer Ingelheim International GmbH or one or more of its affiliated companies. All rights reserved.

This document may not - in full or in part - be passed on, reproduced, published or otherwise used without prior written permission.

primary endpoint, i.e., the composite of recurrent symptomatic VTE and unexplained death (HR 0.08 (95% CI 0.02, 0.25,  $p < 0.0001$  for superiority)). There were only two patients (0.3%) in the dabigatran etexilate treatment group, and none in the placebo group, who had confirmed major bleeding events (HR could not be calculated because of the absence of MBE events in the placebo group). The hazard ratios comparing dabigatran etexilate to placebo for centrally adjudicated clinically relevant bleeding events, measured 2.92 (95% CI, 1.52, 5.60), and any bleed events, measured 1.82 for dabigatran etexilate versus placebo are 2.92 and 1.82 (1.23, 2.68), with  $p$  values for both being  $< 0.003$ .

Based on the adult VTE treatment trials (RE-COVER and RE-COVER II) conducted in over 5000 patients, the incidence of major bleeding events was lower in the dabigatran arms relative to warfarin (hazard ratio DE/W 0.48; 95% CI 0.29 to 0.78) with similar efficacy; primary efficacy endpoint hazard ratio DE/W 1.09; 95% CI 0.77-1.53 ([U09-1400-01](#) and [U11-2298-01](#)). Therefore, this study may have the potential to provide a real therapeutic benefit to participating patients at an individual level.

The planned study may also help to bring new and innovative therapy to paediatric patients with risk of secondary VTE, providing a general benefit to society and to the paediatric patient population.

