#### Clinically relevant non-major (CRNM) bleeding:

- Overt bleeding for which a blood product is administered and which is not directly attributable to the patient's underlying medical condition
- Bleeding that requires medical or surgical intervention to restore haemostasis, other than in an operating suite.

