#### Minor bleeding:

- Minor bleeds are any overt or macroscopic evidence of bleeding that does not fulfil the criteria for either major bleeding or clinically relevant, non-major bleeding.

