#### 7.3.1 Primary analyses

The primary analyses will be based on the primary safety endpoints. The recurrence of VTE, major bleeding events, minor (including clinically relevant non-major (CRNM)) bleeding events, overall mortality and mortality related to thromboembolic events will be analysed as time-to-event and will be summarized by Kaplan-Meier estimates. The rate of occurrence of events at 6 and 12 months will also be provided by K-M estimation. Patients who do not have any of the events or drop out early will be considered as censored for this analysis. Additionally, descriptive rate with number of patients with event divided by total treated patients will also be provided. Early drop out and lost-to-follow-up will be considered as non-event. The components of the composite event will be summarized as below:

- Recurrence of venous thromboembolism will be summarized by Kaplan-Meier estimate of time to first recurrence of VTE. The rate of recurrence at 6 and 12 months will also be provided by K-M estimation. Patients, who do not experience recurrent VTE by the time of analyses, drop out from the study, or die from non-VTE related cause will be considered as censored. The descriptive rate of number of patients with event divided by total treated patients will also be provided. Early drop out and lost-to-follow-up will be considered as non-event when calculating the descriptive rate.
- Major bleeding and minor (including clinically relevant non-major (CRNM)) bleeding will be analysed by K-M estimate of time to first occurrence as competing events. The K-M rate estimate at 6 and 12 month will be provided. The descriptive rate will also be calculated by dividing number of patients with major / minor bleeding by the number of total treated patients. Early drop out, lost-to-follow-up and non-bleeding related death will be considered as non-event and censored.

Proprietary confidential information.

© 2019 Boehringer Ingelheim International GmbH or one or more of its affiliated companies. All rights reserved.

This document may not - in full or in part - be passed on, reproduced, published or otherwise used without prior written permission.

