### 7.3.3 Safety analyses

The safety analyses will be descriptive in nature and will be based on BI standards. Parameters to be evaluated for safety are described in [Section 5.2](#).

AEs will be coded using the MedDRA dictionary. All AEs will be classified according to the following trial periods: screening, treatment, safety follow-up. All AEs with an onset date / time after administration of trial medication up to 3 days after the last intake of study medication will be assigned to the treatment period for evaluation. In addition, AEs with onset date before start of the trial treatment but with worsening in intensity during the treatment will also be assigned to the on-treatment period. Other AEs will be assigned to the screening or post-treatment period, respectively. All AEs (including bleeding) in the treatment period will be tabulated in total and according to seriousness, severity and possible relationship to trial medication. AEs in the screening or follow-up period will be listed.

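### The primary bleeding endpoint and Section 7.3.1 pool CRNM with minor bleeding, against the definition in 5.2.1, and the first-occurrence rule can hide a later, graver bleed

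*Protocol*

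**What the plan says.** The synopsis and Section 5.2.1 list the primary bleeding endpoint as "Major and minor (including clinically relevant non-major (CRNM)) bleeding events at 6 and 12 months". Section 5.2.1 then defines three grades. Major has its own criteria. CRNM covers overt bleeding for which a blood product is given and which is not directly due to the underlying condition, and also "Bleeding that requires medical or surgical intervention to restore haemostasis, other than in an operating suite". Minor is any overt bleeding that "does not fulfil the criteria for either major bleeding or clinically relevant, non-major bleeding".

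Section 7.3.1 names two bleeding groups, major and minor including CRNM, and says that they "will be analysed by K-M estimate of time to first occurrence as competing events", with Kaplan-Meier (K-M) rates at 6 and 12 months. The crude rate is obtained by "dividing number of patients with major / minor bleeding by the number of total treated patients".

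Outside the primary analysis, Section 7.3.3 states: "All AEs (including bleeding) in the treatment period will be tabulated in total and according to seriousness, severity and possible relationship to trial medication". Section 3.1.1.2 has all elements of the primary endpoints confirmed or refuted by an independent committee. Section 6.2.2 requires an Unscheduled Visit for major or clinically relevant bleeds, so sites must already recognise the CRNM grade.

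**The concern.** Under the definitions a CRNM bleed cannot be minor; under the endpoint and the analysis section it is. The label matters because Section 7.3.1 builds its rates on it. A bleed that needed a blood product, or an intervention to stop it, falls in the same group as any small nosebleed, and only the first bleed in that group counts.

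The competing-events wording adds a second problem. If a first bleed of either kind ends a child's contribution, an early minor bleed removes that child from the estimate of major bleeding.

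This is a safety trial of about 100 children in which major bleeds will be few. The bleeding summary would then rest on a sparse major-bleed rate and a non-major rate from which clinically relevant bleeding cannot be read.

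**Working it through.** 1. **The plan's own figures.** Section 7.6 gives the probability of at least one event among 100 patients as 1 − (1 − p)^100. At p = 5% this is 99.4% (stated: more than 99%), and at p = 1% it is 63.4% (stated: higher than 63%). The Wilson intervals in Table 7.6:1 reproduce within rounding, except the upper limit at 4% (9.84 computed, 9.89 printed), which does not affect this point.

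2. **The three texts side by side.** In 5.2.1 the grades are mutually exclusive, because minor is whatever meets neither of the other two sets of criteria. The endpoint in 5.2.1 and the synopsis has two components, with CRNM inside minor. Section 7.3.1 uses the same two components for both K-M and crude rates. The adverse event tables in 7.3.3 split by seriousness, severity and relationship, not by bleeding grade.

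3. **What the counting rule does to individual children** (constructed examples):

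| Child | Bleeds by 5.2.1 grade | Minor-including-CRNM curve | Major curve |
|---|---|---|---|
| A | minor in week 2, CRNM in month 5 | event in week 2 only | no event |
| B | minor in week 2, major in month 5 | event in week 2 | no event if the first bleed of either kind ends follow-up; event in month 5 if each group has its own first event |
| C | minor in week 2 only | event in week 2 | no event |

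A and C give identical results, so A's CRNM bleed leaves no trace in the 7.3.1 output. B's major bleed depends on how competing events is read. Under the stricter reading, B is absent from the major curve but still counts in a crude rate of patients with a major bleed, so the two planned figures could disagree.

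4. **What the pooled rate can say about CRNM.** Suppose 20 of 100 children have at least one non-major bleed. The planned result is 20%, interval 13.3 to 28.9 (Table 7.6:1). The number of them with a CRNM bleed can be anything from 0 to 20. With 2, the CRNM rate is 2% (0.55 to 7.00); with 10, it is 10% (5.52 to 17.4). The pooled result is the same in both cases. The 20 is only an illustration, since the protocol gives no CRNM or minor-bleed rate, but the ambiguity exists for any pooled count above zero.

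5. **How sparse major bleeding may be.** Section 2.3 cites major bleeding in 0.5% to 1.7% of anticoagulated paediatric patients. If that held here, 100 children would give 0.5 to 1.7 expected major bleeds. The chance of seeing any would be 1 − 0.995^100 = 39% to 1 − 0.983^100 = 82%. At such counts, losing one major bleed to an earlier minor one could remove the only event.

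**The case against.** The strongest reply is that this is mainly a labelling matter. The parenthesis tells the reader that the endpoint's second component is wider than the definition, every bleed still receives a grade under 5.2.1, and the endpoint was agreed with the Paediatric Committee. A breakdown by grade could stand in the statistical analysis plan, which is not shown. The opening of 7.3.1 also lists major and minor bleeding as separate time-to-event variables, which favours the milder reading for child B. Part of this stands: the endpoint need not change, no bleed goes unrecorded, and the loss of a major bleed is a possible reading rather than a certain one. But 7.3.1 does more than leave detail open. It fixes a grouping and a first-event rule, and that grouping conflicts with 5.2.1.

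A reader might infer three stronger claims, which the documents do not support.

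- *Clinically relevant bleeding is never estimated.* Major bleeding, its gravest part, has its own planned rate, and the analysis plan may add the rest. Only the protocol text can be said to lack a CRNM or major-plus-CRNM rate.
- *Pooling conceals a threefold rise in CRNM that separate rates would reveal.* Assume 20% of children have only minor bleeds. CRNM of 2% or 6% then gives pooled rates of 22% (15.0 to 31.1) or 26% (18.4 to 35.4), which overlap widely. At CRNM 2%, an assumed 10% or 30% with only minor bleeds gives 12% (7.0 to 19.8) or 32% (23.7 to 41.7). But the interval for CRNM alone at 2%, 0.55 to 7.00, also contains 6%, so the separate rate would not settle it either. The trial has no control group and no hypothesis test, so there is no reference rate for a rise.
- *Pooling prevents comparison with the adult hazard ratio of 2.92 for clinically relevant bleeding in Section 2.3.* That ratio is against placebo. A single-arm trial gives no hazard ratio however bleeds are grouped. In the same adult trial any bleeding also showed an excess, at 1.82 (1.23 to 2.68).

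**Conclusion.** The point holds as an inconsistency with a consequence for the analysis. The endpoint and Section 7.3.1 count CRNM as minor, against the definition in 5.2.1. The first-occurrence rule lets a trivial bleed hide a later CRNM bleed, and under one reading of competing events it may also remove a later major bleed. The protocol plans no rate for CRNM or for major plus CRNM.

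The size cannot be fixed from the protocol, because it gives no CRNM or minor-bleed rate and no frequency of repeat bleeds. What can be said without such rates is that the pooled result leaves the CRNM rate anywhere between zero and the pooled rate itself. The sample size is unaffected, since the composite in Section 7.6 counts major bleeds only. The gain from correction is a readable rate of clinically relevant bleeding; it does not make modest differences detectable in 100 children.

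**What to change.** Keep the agreed endpoint, but state in the synopsis, 5.2.1 and 7.3.1 that its second component means all non-major bleeding, that is CRNM or minor as defined in 5.2.1.

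In 7.3.1 add 6- and 12-month time-to-event and crude rates, with confidence intervals, for four groups: major, CRNM, major or CRNM, and any bleeding. Count each from the patient's own first event of that grade, whether or not a lesser bleed came earlier. Reword the competing-events sentence so that a minor bleed does not end risk for a CRNM or major bleed.

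The cost is a few extra summaries. The grades are already defined and the events already go to adjudication, so no patients or visits are added. The one point to confirm is that the grade of each bleed is recorded with the adjudicated result, because Section 3.1.1.2 speaks only of confirming or refuting events. The CRNM intervals will be wide: at an observed 2% in 100 patients, 0.55 to 7.00.

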##### Secondary endpoints:

- Occurrence of post-thrombotic syndrome (PTS) at 6 and 12 months  
An appropriate instrument (e.g. the Manco-Johnson Instrument or Villalta scale or a similar instrument; the chosen instrument will be available in the ISF)
- Pharmacodynamic assessments (central measurement of dTT (Anti-Factor IIa activity), aPTT and ECT) at Visit 3 (after at least six consecutive dabigatran etexilate doses) and after at least 3 days following any dabigatran etexilate dose adjustment
- Number of dabigatran etexilate dose adjustments during treatment period (i.e. Number of patients with dabigatran dose adjustments during treatment period)

